6. METHODS

6.1. CTI CLINICAL PROGRAM & ITS PROCESSES (only for the INTERVENTION GROUP)

We are adapting a validated and widely used program for a new setting. The only revision is to minimize the coaching in the ED to avoid prolonging the patients' discharge process as that would notably impede ED operations, inhibiting dissemination and implementation. Thus, the review of the four pillars of the CTI model, which is typically covered in the hospital, will occur during the first home visit, which will ideally occur within 24-48 hours.

Figure 3: Care Transitions Intervention Processes

Paramedic Coach Identification: The paramedic coaches will be considered part of the research team and will be fully trained in accordance with the UW IRB and UR IRBs. Participating paramedic coaches will be identified and selected to participate based on their level of EMS experience and their interest in the research objectives. The paramedic coaches will be paid as subcontracted providers by the UW Dept. of Emergency Medicine. They will not have an appointment registered with the University of WI Human Resources. Therefore an Individual Investigator Agreement (IIA) will be completed for each paramedic coach. IIAs have been obtained and the requisite human subjects training for each coach has been completed. The paramedic coaches are now officially included as members of the study team and listed on the 'key personnel' and 'roles' pages of the protocol application.

Training: The paramedic coach will be trained following the existing national standard created by [name]. The paramedic staff will complete the on line training, then go to Denver, CO to receive the full training, and then will shadow coaches in Rochester, NY and Madison, WI to better understand the process. The coaches will also take part in the monthly training updates that are delivered by [name] CTI staff via webinar.

Processes:

After the patient returns home, the paramedic coach will perform the home visit, within 24-48 hours ideally. During this visit, the coach will follow the program as they have been trained by [name] and his staff. They will coach the patient to reconcile medications; emphasize the importance of provider follow-up and practice obtaining an appointment and asking the PCP questions at the visit; review red flags due to medications and the acute condition; and develop the Personal Health Record. As per the CTI, the paramedic will not do the work for the patient, but will coach and educate the patient and/or caregiver. During the CTI program's follow-up calls (up to 3, not related to research activities), the paramedic coach will further coach and support the patient and/or caregiver.

If the subject expresses need for assistance beyond coaching or the coach identifies clinical issues, then he/she will coach the subject to call his/her provider to obtain further guidance. If the subject is unable to do so, then the paramedic coach will call the PCP directly or 911 to request an ambulance for evaluation and transport to an ED. Because the coach is a paramedic and has extensive medical training, he/she has the expertise to recognize medical issues and summon assistance.

All CTI program documentation will be securely retained within the study files in the UW Department of Emergency Medicine and the UR Department of Emergency Medicine. If the patient subject consents to the communication, a status summary will be sent to their primary care provider for inclusion in their medical record. This information will be sent using secure, HIPAA compliant email systems. Because all UW enrolled subjects will be patients of UWHealth, the UW email system will be used and is HIPAA compliant. Because all UR enrolled subjects will be patients of UR Medicine, the UR email system will be used and is HIPAA compliant.

6.2. USUAL CARE (CONTROL) GROUP

The usual care group patients will receive the routine UW and UR discharge educational materials from the ED staff. There may be an effect from the research survey calls, but that would only decrease the magnitude of the anticipated differences between the control and intervention group.

6.3. RESEARCH PROCESSES

The informed consent, baseline survey and randomization will be completed in the ED by the study RA. To facilitate scheduling the coach home visits the RA will know the coach's weekly availability. For those subjects randomized to the intervention group, the RA will schedule the coach home visit within 24 hours of ED discharge ideally and then send the paramedic coach the appointment time, patient's contact information and ED discharge summary via email. To ensure that all PHI is communicated securely, UW coaches will be provided with UW Department of Medicine email addresses and at UR the coaches will also be provided with UR email addresses. Thus, all communication will be within each institution's secure, HIPAA compliant email system.

Blinded research staff will be responsible for all research surveys for the patient and caregiver. These are intended for all subjects (control and intervention group) and independent of the clinical CTI program delivered to the intervention group.

Patient subjects will be contacted four days after ED discharge. The RA will telephone the subject and complete a survey that evaluates the program fidelity and initial outcome measures (Table 2). We chose this time point because patients should have made medication changes (e.g., started an antibiotic) and contacted their provider for follow up by then. We anticipate that the survey will take no longer than 10 minutes to complete.

Patient subjects will be re-contacted thirty days after ED discharge. The RA will re-contact all subjects and complete a final survey. We anticipate that the survey will take no longer than 10 minutes to complete the telephone survey. The RA will inform subjects of the research phone numbers from which all calls will be made. It is anticipated that providing this information will re-assure subjects and give an increase sense of comfort knowing who is calling them.

If, at the time the follow-up assessments are due (Day 4 and Day 30) the patient subject is either in the ED or inpatient in the hospital, research staff will go to the ED or inpatient hospital floor and request permission from the attending health care provider to visit the patient to complete the followup survey. If the provider states the research visit is inappropriate the RA will leave the ED/inpatient area immediately. The patient subject can decline the RA visit and study survey at any time. This change in data collection does not apply to the Caregiver subject.

Caregiver subjects will be re-contacted thirty days after ED discharge. The RA will re-contact all subjects and complete a final survey. We anticipate that the survey will take no longer than 10 minutes to complete the telephone survey. The RA will inform subjects of the research phone numbers from which all calls will be made. It is anticipated that providing this information will re-assure subjects and give an increase sense of comfort knowing the who is calling them.

The RA will conduct a medical record review at the end of the study. We have built a lag time because we recognize that it can take months for the medical record to be fully updated with care episodes, discharge diagnoses, etc. The collected data are represented in Table 2.

Records Management: All data will be maintained initially on paper and then entered in REDCap, an electronic data management system on a secure server maintained by the UW Department of Medicine. The PI and coordinator are responsible for monitoring data quality in conjunction with the study team. Reports will be generated and reviewed regularly to show the status of all subjects and bring forward any problems with study processes and data completeness.

Individuals who decline to participate will not have any identifiable information retained. We will retain the following variables to compare those participating to those who decline to participate: 1) age up to 89 years and age range for subjects ≥ 90 years, 2) sex, 3) race, 4) chief complaint, 5) reason for declining study participation.

All documentation will be stored in the UW or UR Department of Emergency Medicine locked office space. No later than the end of the study, the forms will be scanned and stored on secured network drives at UW and the paper copies will be destroyed.

Table 3: Schedule of Activities

Paramedic-coached ED Care Transitions to Help Older Adults Maintain their Health								
↓ Activity → Day	0	1	2	3	4	5		30
Recruitment								
Patient and Caregiver (CG) Identified, Recruited & Randomized in ED								
Research Activities								
Control & Intervention Groups								
Patient Baseline & Follow-up Survey Calls								
CG Baseline & Follow-up Survey Calls								
Clincial Activities								
Intervention Group								
Coach Homevisit								
Coach Follow-up Patient Calls - TBD								

EFFICACY ASSESSMENTS

To evaluate the program, the RA who calls the subject will complete the following measures:

1. Care Transitions Measure: The CTM includes the 3 major domains that patients have identified as critically important to their experience with coordination out of the hospital. This will serve as a proxy measure for actual changes.
2. Medication Changes: Survey asking if medication changes are implemented (e.g., new medications started, old medications stopped). If not applicable, then that will be recorded. The date of change will also be queried.
3. Understanding of Red Flags: The discharge instructions from the ED will be abstracted for key red flags. Subjects will be asked to list the red flags for which they are monitoring their condition, and will be asked to explain the meaning of the red flag. The RA will record the subject responses verbatim. Two physicians will review the responses and score the level of understanding on a Likert scale.
4. Follow up with PCP: PCP follow up will be assessed in three different manners. The primary measure will be the time to in-person PCP follow-up (e.g., clinic or home visit). The secondary measures will be time to any PCP follow up (e.g., in-person or phone) and the third approach will be contact with PCP within the time recommended by the ED (e.g., phone or in person) follow-up.
5. Patient Self Efficacy: Wallston’s Perceived Health Competency Scale (PHCS) is a domain-specific

measure of self-efficacy. It assesses perceptions of self-efficacy specific to health-related situations but is not limited to any single behavior.

6. Patient Activation Measure: The Coleman Patient Activation Measure will be the primary measure for this assessment. A 1 point change in score is considered clinically significant for the Coleman measure.

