2. PURPOSE OF THE STUDY AND BACKGROUND

2.1. PURPOSE OF THE STUDY & AIMS

The emergency department (ED) is an important source of acute care for the 40 million older adults (age \geq 65) living in the US. In 2010, older adults made 20 million ED visits, 11 million of which resulted in the patient being discharged home.¹ Older adults do poorly after being discharged home from the ED, with approximately 20% of these patients needing a repeat ED visit within 30 days.^{2,3,4,5,6,7,8,9,10} ***With the older adult population doubling by 2040, the frequency of these adverse events will increase unless interventions improve older adults' ED-to-home transitions.***

Frequent hospital readmissions led to the development, validation, and widespread implementation of the Coleman Care Transitions Intervention (CTI) to improve the hospital-to-home transition.^{11,12,13} In contrast, only a few programs have been tested to improve ED-to-home transitions for older adults, which are almost as frequent as hospital-to-home transitions (11 vs. 13.5 million/year).¹⁴ Unfortunately, these ED-focused programs have demonstrated little success.^{15,16,17,18,19,20,21,22}

Our multi-disciplinary team, which has a history of successful academic-community collaborations to study the care delivered to acutely ill older adults, includes researchers and community partners. Building upon our extensive experience in geriatric emergency medicine and prehospital medicine, as well as Coleman's work, we will apply the CTI to the ED setting, utilizing ambulance-based paramedics to improve the ED-to-home transition. ***Overall, we hypothesize that our community-based, paramedic-***

coordinated, patient-centered, ED-to-home CTI program will improve older adults' post-ED outcomes. We will test this hypothesis in four aims:

1. Implement a community-based, paramedic-coordinated, patient-centered, ED-to-home CTI program in Madison, WI and Rochester, NY for older adults treated in the ED and discharged home.
2. Assess the process outcomes of our ED-to-home CTI program for older adults treated in the ED and discharged home, as compared to usual care.
Hypothesis 1A: More CTI participants will demonstrate understanding of their ED discharge instructions, red flags that indicate a worsening of their condition, and how to respond to the red flags four days after ED discharge.
Hypothesis 1B: More CTI participants will implement medication changes made in the ED within four days of ED discharge.

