3.3. RATIONALE FOR INTERVENTION

We will implement and test the CTI for the intervention group because of its demonstrated effectiveness and cost-effectiveness, its applicability to the ED patient discharged home, its efficiency, particularly relating to activities in the ED, and its widespread use. We have chosen to use community-based

paramedics as the coaches for the CTI because these individuals are highly trained, available in all communities, and are highly respected by patients. Thus, paramedics are able to perform these visits in follow up to ED visits rapidly. Given that the CTI program has been tested using lay people, trained paramedics should be able to perform the required duties.

Table 2: Measures

	Measures	Time	Source/Approach
1. Demo -	Patient age, gender, marital status, race, ethnicity, education level, primary language, home ownership, living status, home address	ED	Patient survey
	Patient relationship with PCP	ED	Patient survey
	Insurance plan / number	ED	Epic review
	Primary Care Medical Home certification level	ED	Health systems
2. Clinical	New home services (since ED visit)	Day 30	Patient survey
	ED medications prior to assessment, chief complaint, final diagnosis (ICD-10), discharge medications, and instructions	ED	Epic review
	CTI Coaching & Services Forms* Personal Health Record (PHR) Home Visit/PHR Discussion Checklist Follow-up Phone Calls Checklist Patient Activation Assessment Medication Discrepancy Tool Care Transitions Measure - 3	CTI Coach home visit & coach follow up calls	CTI program records
3. Covariates	Medical history, including Charlson Comorbidity Index	ED	Patient survey
	Healthcare: Medications, home services, ED / hospital use	ED	Patient survey/ Epic review
	Health Status: Short Form-12 ⁶⁸	ED	Patient survey
	Disability Status: ADL ⁶⁹	ED	Patient survey
	Cognition: Short Blessed Test (BOMC)	ED	Patient survey
	Social Isolation: PROMIS Social isolation short form	ED	Patient survey
	Depression: PHQ-9	ED	Patient survey
	Anxiety: GAD-2	ED	Patient survey
Health literacy	ED	Patient survey	
4. Outcomes			
	Family Caregiver Activation in Transitions	ED, Day 30	Caregiver survey
	Understanding of red flags	Day 4	Patient survey
	Medication changes implemented	Day 4	Patient survey
	Follow up with PCP, specialists, urgent care	Day 4, 30	Patient survey / Epic review
	Wallston's Perceived Health Competency Scale (PHCS)	ED, Day, 30	Patient survey, Caregiver survey

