12.2 PLANNED STATISTICAL ANALYSIS

Through the analytic methods used in Aims 2 and 3, we will assess differences between groups related to process outcome measures (Aim 2) and will assess the effectiveness and cost-effectiveness of the ED-to-home CTI (Aim 3). In Aim 4, we will identify predictors of repeat ED use among intervention group subjects. We will characterize of our study sample using descriptive statistics and corresponding measures of variation. We will assess for differences between groups at baseline despite randomization in key characteristics (e.g., demographics, comorbidities) using t-tests for continuous variables and Chi-square tests for categorical variables, using Fisher's exact test where appropriate. These comparisons will enable the identification of covariates to be controlled in our multivariable analyses. If distributional assumptions associated with a particular statistical procedure are violated, we will use appropriate transformations or non-parametric alternatives. Primary analyses will be performed under the intent-to-treat principle, keeping subjects in the group to which they were originally randomized, regardless of compliance or adherence to study procedures. We will conduct sensitivity analyses among subjects who complete all study procedures to evaluate the effect of the intervention among those who complete all study-related procedures. Hypothesis-driven comparisons will be made to control the family-wise type I error rate at 0.05 (two-sided) for the primary hypothesis.

Caregiver Subject Analysis: Although not an original aim of the study, we have obtained permission from the NIH and will perform a limited analysis of caregiver activation. This was only recently added to

the CTI. To compare the caregiver activation between the control and intervention groups, we will administer the FCAT. The FCAT will be scored as 1-6 points per question, for a score ranging from 10-60. We assume that 30% of participants will have caregivers with them, the average score will be 30, and we will look for a 5 point difference. Our sample size will allow a power of >0.8 for a t-test ($\alpha=0.05$).

Hyp 1A: More program participants will demonstrate understanding of their ED discharge instructions, red flags that indicate a worsening of their condition, and how to respond to the red flags three days after ED discharge.

Hyp 1B: More program participants will implement medication changes made in the ED within three days of ED discharge.

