
Hyp 1C: Program participants will have shorter time-to-follow-up with their primary care physicians.

Hypothesis 1A & 1B: Binary outcomes such as patients' understanding of their ED discharge instructions, red flags and how to respond, and accurate implementation of medication changes, will be compared between intervention and control group using chi-square tests. Estimates of differences between study groups and associated 95% confidence intervals will be provided overall and by study site. A separate multivariable logistic regression model will also be fitted for each of the outcome variables in hypotheses 1A and 1B. This will allow us to evaluate the effect of the intervention on each of these outcome variables while controlling for potential confounding variables, if necessary. **Hypothesis 1C:** Time-to-follow-up visit with primary care physicians will be compared between groups using the Log-Rank Test. Cox regression model will be fitted to compare the survival function after adjusting for potential confounding variables such as demographics, comorbidities etc., if necessary. A hazard Ratio and 95% confidence interval will be estimated. Because we have the issue of competing outcomes present (rehospitalization and follow up), we will have to account for it through the cumulative incidence function.⁷²

Hyp. 2A: Program participants will have increased patient activation 30 days after discharge.

Hyp. 2B: Program participants will have lower odds of repeat ED use within 30 days of discharge.

Hyp. 2C: Program participants will have lower estimated healthcare costs within 30 days of discharge.

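### Hypothesis 1B is measured by patient survey alone, and nothing ties 'not applicable' or the denominator to the ED record, so the arms could be compared on differently selected patients

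*Combined protocol and SAP*

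**What the plan says.** Section 2.1 states Hypothesis 1B as "More CTI participants will implement medication changes made in the ED within four days of ED discharge". Section 12.2 repeats it with a different window: "More program participants will implement medication changes made in the ED within three days of ED discharge".

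Section 6.3, Efficacy Assessments, item 2, gives the measure: "Survey asking if medication changes are implemented (e.g., new medications started, old medications stopped). If not applicable, then that will be recorded". The lead-in says that the RA who makes the call completes these measures. It does not say whether the patient, the RA or the chart decides that a change does not apply.

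Table 2 (Section 3.3) lists "Medication changes implemented" at day 4 with the patient survey as its only source. The next row, follow-up with the PCP and others, lists the survey together with Epic review. In its clinical block, Table 2 also collects "ED medications prior to assessment, chief complaint, final diagnosis (ICD-10), discharge medications, and instructions" by Epic review at the ED time point. Section 3.2 says in general terms that discharge information is gathered for assessing outcomes, without naming 1B.

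Section 12.2 includes "accurate implementation of medication changes" among the binary outcomes to be compared by chi-square test and logistic regression. It gives no denominator and no rule for not-applicable answers.

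Section 6.1 says of the coaches, who see the CTI arm only: "They will coach the patient to reconcile medications". This happens at a home visit planned ideally within 24 to 48 hours.

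**The concern.** 1B makes sense only for patients whose medication was changed in the ED. Membership of that group is fixed at discharge and should not depend on anything that happens later. As written, the only named source for the outcome is an interview on day 4, and the not-applicable category sits inside that interview.

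A patient who never grasped that a drug was started or stopped can reasonably answer that the question does not apply. That patient is among the clearest failures 1B is meant to count. If the answer sets the denominator, the analysed group is selected after randomisation by something the intervention is designed to change, because the coach goes through the medications before the interview in one arm only.

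Keeping patients in their randomised arm does not repair this; it says nothing about who within each arm is counted. Blinded callers (Section 6.3) do not help either, since the difference comes from the respondent. At stake is whether 1B can show that coaching improves the carrying out of medication changes.

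**Working it through.** **No figure to reproduce.** The documents give no expected rate, effect size, denominator or power for 1B. What follows is first a reading of the text, then an illustration in which every rate is assumed.

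**Step 1: is there a link to the chart?** Item 3 of the same list (red flags) states that the ED discharge instructions are abstracted and that two physicians score the patient's recalled answers. Item 2 (medication changes) has no abstraction step. Table 2 names Epic as a source for PCP follow-up but not for medication changes. The Epic data needed are collected, but no section connects them to 1B.

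**Step 2: can a survey-only not-applicable answer be analysed sensibly?** It mixes patients with no change ordered and patients who missed a change.
- Excluded: those who missed a change leave the denominator.
- Counted as failures: patients with no ED change are scored as failing.
- Counted as successes: those who missed a change are scored as adherent.

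Only an outside record separates the two groups, so the gap matters whichever handling is chosen.

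**Step 3: size if such patients are excluded (assumed inputs).** Let p be the true implementation rate among patients with an ED change, and u the share of non-implementers recorded as not applicable. Then

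observed rate = p / [p + (1 − p)(1 − u)].

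| True rates, control / CTI | u, control / CTI | Observed control | Observed CTI | Observed difference |
|---|---|---|---|---|
| 70% / 80% | 25% / 10% | 0.70/0.925 = 75.7% | 0.80/0.98 = 81.6% | +6.0 points |
| 70% / 80% | 50% / 15% | 0.70/0.85 = 82.4% | 0.80/0.97 = 82.5% | +0.1 points |
| 70% / 70% | 50% / 15% | 0.70/0.85 = 82.4% | 0.70/0.955 = 73.3% | −9.1 points |

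**Step 4: a second set of assumptions.** Write w = (1 − p)u, the share of all patients with a change who drop out, so that the observed rate is p/(1 − w). Take true rates of 60% and 70%.

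| w, control / CTI | Observed rates | Observed difference |
|---|---|---|
| 0 / 0 | 60.0% / 70.0% | +10.0 points |
| 10% / 10% | 66.7% / 77.8% | +11.1 points |
| 10% / 5% | 66.7% / 73.7% | +7.0 points |
| 15% / 5% | 70.6% / 73.7% | +3.1 points |
| 20% / 5% | 75.0% / 73.7% | −1.3 points |

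With no true effect (70% in both arms), equal dropout of 10% gives a difference of 0; 10%/5% gives 77.8% against 73.7%, or −4.1 points. The distortion under the null comes from unequal dropout, and more dropout among controls works against the CTI.

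**Step 5: effect on power.** Section 12.1 gives 860 evaluable patients per group, for Hypothesis 2B. Borrow that number and assume half had an ED change: 860 × 0.5 = 430 per arm. For 60% against 70%, power is about 87% on the full group, 58% at w = 10%/5% and 16% at 15%/5%. If 30% to 70% of patients had a change, the ranges are 66% to 95%, 39% to 73% and 11% to 21%.

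**The case against.** The strongest reply is that the text is silent rather than wrong. Item 2 summarises a survey form that is not in the documents. It says that not applicable is recorded, not that the patient decides it, and nothing says that such patients are excluded. 1B concerns changes made in the ED, Section 12.2 speaks of accuracy, and discharge medications come from Epic, so staff may intend to set applicability from the chart. This stands. A reader might infer that the denominator is self-declared by design and that 1B is therefore biased; the documents support neither as a fact.

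The difference between arms is also not shown. Controls receive routine discharge education (Section 6.2), the home visit is early only ideally, and a patient who did not make a change may simply answer no. Section 2.2 says that medication changes may be poorly understood but gives no rate of unawareness and none by arm. This too stands, so the bias must be stated as conditional.

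The reply does not remove the gap. Table 2 states a source for this outcome, and it is the survey alone; where Epic is a second source, as in the next row, the table says so. Followed as written, the plan cannot tell a change that was never ordered from one that was missed.

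**Conclusion.** The point holds in conditional form. 1B is measured only by the day-4 survey, and neither not applicable nor the denominator is tied to the ED record. If applicability follows the patient's answer, patients unaware of a change may be lost or misclassified, and reconciliation in the CTI arm alone can make this unequal.

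The likely direction is against the CTI: a benefit hidden or, under the more extreme assumptions, reversed. It does not point to a false claim of benefit. The size is unknown. In Step 3 a true +10 points is observed as about +6 to about 0; the wider set in Step 4 runs from +11.1 to −1.3. All rates in both are assumptions.

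The consequence is limited. 1B is a process outcome, and Section 12.1 sizes the trial on 2B, although Section 3.2 counts process measures among the primary outcomes. The change is worth making because it is cheap and the data are already planned.

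**What to change.** Amend Section 6.3 item 2, Table 2 and Section 12.2 as follows:

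1. Define the 1B population, blind to arm, as patients whose Epic ED discharge medications and instructions show a drug started, stopped or changed. Add Epic review as a source for this outcome in Table 2.
2. Ask the day-4 question by open recall. Do not read the abstracted list to the patient: that could prompt controls, and Section 6.2 already accepts that survey calls may shrink the difference between groups.
3. Compare the answers with the abstracted list blind to arm. Count a patient with a documented change who reports none, or not applicable, as not implemented. Use not applicable only when Epic shows no change.
4. State one binary rule per patient, for example that all documented changes were implemented, and one time window, since Sections 2.1 and 12.2 differ (four and three days).
5. Report the survey-only definition as a sensitivity analysis.

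The cost is wording plus some abstraction and matching work. The reported implementation rate will be somewhat lower. Some patients will be misclassified where the ED record is incomplete; Section 2.2 itself cites instructions that omit content such as medication changes (29%). Open recall may also score as a failure a patient who made the change but cannot name it, which could favour the coached arm. The sensitivity analysis shows how far the result depends on the rule.
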